6.6. INFORMATION AND CONSENT

Informed consent will be obtained from eligible patients prior to their enrolment in the trial. Patient Information Consent Form will be signed by the participant and a copy will be provided to the patient/person responsible as well as a copy filed in their medical record. The original consent form will be stored with the study file in a secure locked location.

6.7. RANDOMISATION PROCEDURE

Subjects will be computer randomized using the RedCAP database randomisation module. Members of the research team dispensing or transferring drugs will not be the same team members performing assessments.

Blinding

This study will be double-blinded. All delirium assessments will be conducted by members of the research team not involved in transferring or dispensing study drug. The clinical teams will not be informed of group assignment but may be unblinded if concerns arise about the care of individual patients. The delirium assessment team will always remain blinded to group intervention.

All data analysis will be conducted by separate members of the research team and all information will be de-identified.

6.8. END OF STUDY TREATMENT/WITHDRAWAL PROCEDURE

The study will end 30 days after surgery.

If at the 30-day cognitive screening, there is measured cognitive decline, this will be reported to the PI and if required discussed with the treating medical team, the patient and/or their GP for ongoing care.

6.9. PATIENT WITHDRAWAL

Patients or persons responsible may withdraw through proxy consent or if their treating physician believes it in their best interest to not continue.

7. OUTCOMES

7.1. DEFINITION OF OUTCOMES

Delirium severity will be defined using the Delirium Rating Scale Revised-98 (DRS-R-98)

Delirium incidence will be defined using the 3D-CAM and administered as described.^{32,33}

Acquisition of EEG recordings and quantification of awake EEG SWA (EEG power 0.5-6 Hz) will proceed as published previously by our group.¹⁴

Blood will be processed with quantitation of IL-8 and NfL as we have previously described.³⁴ At Royal Prince Alfred Hospital patients will have CRP, WCC and troponin sent as SOC.

Rates for enrollment will be calculated with denominators of total eligible and total approached for consent. The rate of screen failures will provide information on the surgical volume and coordinator staff required. A high number of study refusals due to concerns of study drug or type/number of outcome assessments will provide valuable information on revising the study design and/or administration of study procedures for a future investigation. Enrollment rates of <25% based on total approached for consent will warrant revision of study design or additional sites in a future larger scale trial.

Rates of adherence will be computed based on the intake of each dose of study drug, with adherence defined as at least 80% of doses taken (4 of 5 total doses). Reasons for not taking study medication will be classified into the following categories: 1) forgetfulness, 2) misunderstanding, 3) interference with medical care, 4) possible side effects, 5) fear/stress, 6) lack of time.

Rates of data acquisition for CAM assessments, EEG recordings, and IL-8 sampling will be compiled at each time point. Less than 90% collection rate for interpretable outcome measures will constitute a “no go” signal, warranting revision of schedule of activities or pipeline for processing biomarkers.

Adverse events (AE) of nausea, diarrhea, headache, and insomnia will be evaluated from evening before surgery through POD 3. A high rate of AEs directly related to the study drug (>30%) combined with an overall adherence rate of <80% will constitute a “no go” signal for a larger clinical trial.

Postoperative pain scores will be determined using the visual analogue scale (VAS)

Patients at RPAH, will have a thromboelastograph sent prior to start of surgery to monitor platelet function.

Change in cognition and disability at 30 days postoperatively

Blood loss

8. STATISTICAL CONSIDERATIONS

8.1. SAMPLE SIZE OR POWER CALCULATION

Based on an estimated 25% enrollment rate, then n=184 screen-positive patients will provide sufficient power to measure this proportion with a 95% confidence interval width of 13%. From our preliminary data, we expect successful enrollment of 46 patients across 2 sites over 9 months. This will allow estimation of the proportion of patients who will complete at least 80% of doses of fluvoxamine with a 95% confidence interval width of 23%, assuming a completion rate of 80%.

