2. HYPOTHESIS

We hypothesize that >25% of approached patients will be enrolled in the study. We also hypothesize that >80% enrolled patients will be adherent to oral fluvoxamine or placebo doses, and >90% of interpretable outcome measures will be obtained.

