6. STUDY PROCEDURES

6.1. STUDY FLOW CHART

Forty-six surgical patients will be randomized 1:1 to a prospective interventional parallel arm double-blinded placebo-controlled trial. All patients will undergo baseline cognitive screening, 3D-CAM assessment, and DRS-R-98 scoring at the enrolment visit. The intervention arm will receive five doses of oral fluvoxamine capsules, 100mg the night before surgery, 100mg twice daily on the day of surgery and on POD 1; pharmacokinetic modeling predicts high sigma-1 receptor binding at POD 1-2, coinciding with anticipated peak delirium incidence.³⁰ A placebo capsule will be administered at the same schedule for those in the control arm.

Outcome measures include: (1) Feasibility: Incidence and reasons for screen failures and withdrawals, (2) Safety/feasibility: incidence/severity/relatedness of adverse events, number/reasons of missed study drug administrations, (3) Feasibility: Incidence and reasons for missed outcome measurements, (4) Feasibility: Delirium incidence/severity (3D-CAM-S) at enrollment, POD 1-4 (both AM and PM), (5) Feasibility: IL-8 and NfL on POD 1 AM and POD 2 AM, and (6) Feasibility: awake EEG SWA on POD 1 AM and POD 2 AM.

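### The 23% confidence interval width for fluvoxamine adherence in section 8.1 is the width for all 46 patients; the roughly 23 who receive fluvoxamine give about 33%

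*Protocol*

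**What the plan says.** Protocol section 8.1 plans for 46 enrolled patients across two sites and says this allows "estimation of the proportion of patients who will complete at least 80% of doses of fluvoxamine with a 95% confidence interval width of 23" per cent, on the assumption that 80% complete.

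Section 6.1 states that "Forty-six surgical patients will be randomized 1:1". It adds that "The intervention arm will receive five doses of oral fluvoxamine capsules" and that "A placebo capsule will be administered at the same schedule for those in the control arm".

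Three other statements bear on adherence:

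- Section 2 sets the target that ">80% enrolled patients will be adherent to oral fluvoxamine or placebo doses".
- Section 7.1 counts a patient as adherent if at least 4 of the 5 study drug doses are taken. It names no arm.
- Section 7.1 also sets a no-go signal for the larger trial: a rate of adverse events directly related to study drug above 30%, "combined with an overall adherence rate of <80% will constitute a" no-go. It gives no denominator for either rate.

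**The concern.** The proportion named in section 8.1 can be observed only in patients who are given fluvoxamine, and 1:1 allocation of 46 leaves about 23 of them. A 23% width at an assumed 80% looks like a calculation on the full 46, so a reader would take the fluvoxamine adherence estimate to be more precise than the design makes it.

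This matters because Aim 2 (section 1.2) is the feasibility of giving perioperative fluvoxamine in a placebo-controlled trial, and the adherence rate feeds the planning of that larger trial.

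The same ambiguity carries into the no-go rule. If its adherence rate is pooled over arms, half the denominator is placebo patients, who cannot miss doses because of the drug's effects. Good placebo adherence could then offset poor fluvoxamine adherence.

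**Working it through.** **Inputs.** Total randomised 46, allocation 1:1, fluvoxamine in the intervention arm only (section 6.1), hence 46/2 = 23 per arm. Assumed completion 80%, 95% confidence, stated width 23% (section 8.1). The protocol states no dropout allowance, so none is applied.

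**Meaning of width.** Section 8.1 also gives 13% for n = 184 at 25%. The full Wald width is 2 × 1.96 × √(0.25 × 0.75/184) = 12.5%, and the exact (Clopper-Pearson) width is 13.0%. Width therefore means full width, not half-width.

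**Reproducing the 23%.** With n = 46: 2 × 1.96 × √(0.80 × 0.20/46) = 2 × 1.96 × 0.0590 = 23.1%. Wilson gives 22.7%. Solving the Wald formula for a 23% width gives n = (2 × 1.96)² × 0.16/0.23² = 46.5. The stated figure is the all-patient figure.

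**Fluvoxamine arm alone.** With n = 23: 2 × 1.96 × √(0.80 × 0.20/23) = 2 × 1.96 × 0.0834 = 32.7%, which is √2 ≈ 1.41 times as wide.

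| Method | n = 46 | n = 23 |
|---|---|---|
| Wald | 23.1% | 32.7% |
| Wilson | 22.7% | 31.5% |
| Jeffreys | 22.7% | 31.6% |
| Agresti-Coull | 23.1% | 32.5% |
| Clopper-Pearson (exact) | about 25% | about 35% |
| Wald, continuity-corrected | 25.3% | 37.0% |

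None of these methods gives 23% with n = 23.

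**No-go rule, adherence component only.** If adherence is pooled, 0.80 × 46 = 36.8, so 37 adherent patients are enough to reach 80%. The protocol gives no placebo adherence; the values below are assumptions.

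- Placebo 21/23: fluvoxamine 37 − 21 = 16/23 (69.6%) is enough.
- Placebo 22/23: 15/23 (65.2%) is enough, since 37/46 = 80.4%.
- Placebo 23/23: 14/23 (60.9%) is enough.

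The chance that observed adherence reaches 80% follows from two independent binomials of 23. The pooled rate needs at least 37/46, the fluvoxamine arm alone at least 19/23.

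| True adherence (assumed): fluvoxamine, placebo | Pooled reaches 80% | Fluvoxamine arm reaches 80% |
|---|---|---|
| 65%, 95% | 56% | 5.5% |
| 70%, 90% | 56% | 14% |
| 70%, 95% | 73% | 14% |

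**Cost of using one arm.** If true adherence is 85% in both arms (assumed), the chance of falling below 80% is P(X ≤ 18 of 23) = 26% in the fluvoxamine arm and P(X ≤ 36 of 46) = 14% pooled. At a true 90% the chances are 7% and 1%.

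**The case against.** The strongest reply is that one phrase is wrong, not the number. Section 2 counts fluvoxamine and placebo doses together, section 7.1 speaks of study drug, and Aim 2 is framed within a placebo-controlled trial. All of this fits pooled adherence, for which 46 is the right denominator and 23% the right width. This stands as a possible reading, and it may be the intended one. It does not remove the conflict, because section 8.1 still attaches the figure to fluvoxamine doses.

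A reader might also infer that pooling lets a poorly tolerated drug through to a go decision more than half the time. The documents do not support that, for four reasons.

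- The rule has two conditions that must both hold, so low adherence alone never triggers it, pooled or not. The 56% and 5.5% are chances that one component clears 80%. They are not chances of a go.
- Section 7.1 does not define overall. Section 2 makes pooling over arms the natural reading, but the word could mean across the five doses.
- Tolerability is not judged by adherence alone. Section 6.2.2 evaluates adverse events in both arms with severity and relatedness, and section 7.1 classifies the reasons for missed doses, including possible side effects. These data lessen the masking concern, but they supply no arm-specific threshold.
- The placebo rates behind the masking figures are assumed.

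Finally, pooled adherence is a legitimate measure of trial conduct. Most of the listed reasons for missing doses, such as forgetfulness, can arise in either arm. Moving the threshold to one arm would change a decision criterion, at the cost shown above. That is a design choice and cannot be presented as a mere correction of wording.

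**Conclusion.** The precision statement is wrong as written. For the quantity it names, the design gives a 95% confidence interval about 33 points wide at 80% completion (31.5 to 37.0 across methods), against the 23 points stated. This rests on 23 fluvoxamine patients with no losses; losses would widen it. If pooled study drug adherence was intended, the number is right and the description is wrong.

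The point about the no-go rule is secondary and conditional. The denominators are not stated, and section 2 points to pooling. Where the adverse event condition is already met, pooled adherence can then hide fluvoxamine adherence in the 60s per cent, given high placebo adherence. The denominator of the 30% adverse event rate is equally open.

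This should be fixed, but it is not critical. The primary endpoint (enrolment rate) and the sample size of 46 are unaffected.

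**What to change.** **Section 8.1.** Replace the adherence sentence with one giving both figures: assuming 80% completion, the 95% confidence interval width is about 23% for study drug adherence pooled over both arms (n = 46), and about 33% for the fluvoxamine arm (n = 23). This changes wording only; the stated precision for fluvoxamine becomes less favourable.

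**Section 7.1.** State the denominator of both no-go conditions, and say whether overall means over arms or over doses. Report adherence and drug-related adverse events by arm beside the pooled rate. This needs no extra patients or procedures.

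**If the sponsor applies the adherence threshold to the fluvoxamine arm.** Record it as a change of criterion and acknowledge the cost: the component would trigger falsely about 26% of the time, against 14% pooled, if true adherence is 85% in both arms (assumed). If the pooled rule is kept, say that it measures trial conduct and read it together with the results by arm.

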8.2. PROVIDE A DETAILED ANALYSIS PLAN

The DRS-R-98 score, 3D-CAMS, TICS-M, Verbal fluency, WHODAS and GDS15 will be analyzed by Mann-Whitney or t-test depending on distribution.

The incidence of delirium (on 3D-CAM), will be analysed by Fisher’s exact test.

EEG analysis will be conducted by pwelch calculation of power bands and Mann-Whitney or t-test depending on distribution.

The biomarkers (IL-8 and NfL [and CRP, WCC and troponin]) will be log transformed and will be analyzed by Mann-Whitney or t-test depending on distribution¹⁵.

Rates of data loss will be established using point estimates and sample variance will be estimated in intention to treat analyses.

For all analyses, a P below 0.05 will be considered statistically significant.

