4.4. ENDPOINTS

PRIMARY ENDPOINTS

Trial enrolment rate

SECONDARY ENDPOINTS

The safety of perioperative flvoxamine
--

The incidence of delirium on POD1–4 (3D-Confusion Assessment Method (CAM) or CAM-ICU)

Severity of delirium on POD 1–4 (Delirium Rating Scale Revised-98 DRS-R-98))
--

Rate of protocol adherence

Rate of completed 3D-CAM assessments

Peak delirum severity on POD1–4

Collection rate of biomarkers (IL-8 + NfL) and EEG recording on POD1+2
--

EEG slow wave activity (0.5–6Hz) on POD1+2
--

POD1+2 changes in IL-8 and NfL

RASS score on POD1–4

Postoperative pain score
Change in cognition and disability at 30 days postoperatively
Blood loss
Thromboelastography on the day of surgery prior to incision at RPAH only
CRP, WCC and troponin

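### Section 8.2 compares the arms on six scales without baseline adjustment, although all six are measured at enrolment, and calls P below 0.05 significant across 13 outcomes in a trial sized only for feasibility

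*Protocol*

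**What the plan says.** Protocol section 8.2 fixes the test for each between-arm comparison:

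- Six scales: "The DRS-R-98 score, 3D-CAMS, TICS-M, Verbal fluency, WHODAS and GDS15 will be analyzed by Mann-Whitney or t-test depending on distribution".
- Delirium incidence: the sentence beginning "The incidence of delirium (on 3D-CAM), will be analysed by" names Fisher's exact test.
- EEG: "EEG analysis will be conducted by pwelch calculation of power bands and Mann-Whitney or t-test depending on distribution".
- Five biomarkers (IL-8, NfL, CRP, WCC, troponin): these "will be log transformed and will be analyzed by Mann-Whitney or t-test depending on distribution".

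It then sets one rule for everything: "For all analyses, a P below 0.05 will be considered statistically significant". It gives no covariate, no order of importance among outcomes, no exploratory label, and no criterion for judging the distribution.

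Baselines exist for all six scales. Section 6.1 states: "All patients will undergo baseline cognitive screening, 3D-CAM assessment, and DRS-R-98 scoring at the enrolment visit". The visit table in section 6.2.1 also marks 3D-CAM-S at enrolment, and its footnote places TICS-M, verbal fluency, WHODAS and GDS15 in the preoperative cognitive screen.

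Section 4.4 lists as an endpoint "Change in cognition and disability at 30 days postoperatively", and section 3.2 has the same item. The synopsis (secondary objective 13) frames cognition, disability and depression as postoperative change. Section 8.2 names only the scales.

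**The concern.** Two features of the stated plan work against a trial of this size.

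First, a t-test or Mann-Whitney test takes one number per patient and cannot use the baseline as a covariate. With 23 patients per arm, information that is already being collected is left unused or, if change scores are analysed, used inefficiently. Because section 8.2 does not say which score enters the test, the quantity being compared is not fixed for four of the six scales. Letting the distribution pick the test opens it further: a t-test goes with a difference in means, while a Mann-Whitney test does not.

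Second, an unqualified significance rule over many secondary comparisons makes it fairly likely that something will be called significant by chance. Section 1.2 says the pilot will serve as preliminary data for a grant application, so a chance finding could be given weight that the design cannot support.

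**Working it through.** **The plan's own figures.** Section 8.1 sizes the trial on interval widths for two proportions. The Wald width is 2 × 1.96 × √(p(1−p)/n).
- Enrolment: p = 0.25, n = 184 gives 12.5% (Clopper-Pearson 13.0%). The stated 13% is reproduced.
- Adherence: p = 0.80, n = 46 gives 23.1%. The stated 23% is reproduced.

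Neither concerns an arm comparison. With 23 per arm, the difference detectable with 80% power at two-sided 5% is 2.80 × √(2/23) = 0.83 SD, unadjusted.

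**Precision.** Let r be the correlation between baseline and follow-up, with equal variances at both times. The protocol gives no r, so the values are assumptions. The variance of the arm difference, relative to comparing final scores, is 1 for the final score, 2(1−r) for the change score and 1−r² for ANCOVA. ANCOVA relative to change is therefore (1−r²)/(2(1−r)) = (1+r)/2.

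| r (assumed) | Final score | Change score | ANCOVA | ANCOVA ÷ change |
|---|---|---|---|---|
| 0.3 | 1 | 1.40 | 0.91 | 0.65 |
| 0.5 | 1 | 1.00 | 0.75 | 0.75 |
| 0.7 | 1 | 0.60 | 0.51 | 0.85 |

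For r between 0.5 and 0.7:
- Against a final score the variance falls by 25% to 51%. The 46 patients then count as 46/0.75 = 61 to 46/0.51 = 90.
- Against a change score it falls by 25% to 15%. The 46 patients then count as 46/0.75 = 61 to 46/0.85 = 54.

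For any r strictly between 0 and 1, ANCOVA has the smaller variance on either reading, apart from the one degree of freedom spent on the baseline slope.

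**Number of tests.** 6 scales + 1 incidence + 1 EEG + 5 biomarkers = 13. Twelve use t or Mann-Whitney and one uses Fisher's exact test.

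**Chance of at least one P below 0.05 with no effect**, one test per outcome:
- Independent outcomes: 1 − 0.95^13 = 48.7%.
- Simulated, with an assumed common correlation of 0.3, 0.5 or 0.7: about 42%, 33% and 24%.

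Fisher's test is conservative, so these figures are slightly high for that one outcome. Testing each day or visit separately would add tests.

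**Choice of test by distribution.** Simulation with 23 per arm, 20,000 runs for each of four distribution shapes:
- A fixed normality pretest followed by t or Mann-Whitney rejected in 4.5% to 4.8% of runs.
- Picking whichever P value was smaller rejected in 5.5% to 6.4%.

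**The case against.** The strongest reply is that this is a feasibility pilot and no decision depends on these P values. The go/no-go signals in section 7.1 are enrolment, outcome collection, and adverse events combined with adherence. Section 1.2 plans the future trial on feasibility rates, on variances of EEG, NfL and IL-8, and on a preset 20% reduction in severity. A reader might infer that the future sample size would be built on the pilot's arm differences; section 1.2 does not support that. This limits the stakes to how secondary results are estimated and described.

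A reader might also infer that the baseline is ignored altogether. That goes too far: for cognition, disability and (in the synopsis) depression the target is change, so the baseline may enter by subtraction. The larger gain, up to 51%, applies only if final scores are tested. For DRS-R-98 and 3D-CAM-S, section 6.4 keeps patients with cognitive dysfunction out, so baselines may sit near the floor and adjustment may add little.

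It may seem that choosing the test from the data inflates the error rate. The simulation does not bear this out for a fixed pretest, and the cost is an open choice of reported quantity. Nor is 49% a firm figure: several outcomes measure the same condition or related inflammatory markers, so they are unlikely to be independent.

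Finally, covariates and effect measures are often left to an analysis plan, which is not at hand here. That would answer a silent protocol. This one names the tests and the significance rule, so an analysis plan would have to depart from the protocol to improve on them.

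**Conclusion.** The point holds in limited form. Section 8.2 prescribes unadjusted two-sample tests for six scales with enrolment measurements, and leaves open whether change or final score is compared for four of them. At an assumed r of 0.5 to 0.7, ANCOVA lowers the variance by 25% to 51% against a final score or 25% to 15% against a change score; for DRS-R-98 and 3D-CAM-S the gain is probably small.

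The rule that P below 0.05 is significant covers 13 outcomes in a trial not sized for any of them. The chance of at least one false positive is roughly 24% to 49%, depending on how correlated the outcomes are. The risk comes from the number of tests, not from the way the test is chosen.

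The documents do not support reading this as a threat to the trial's main purpose. The enrolment estimate and the go/no-go signals are unaffected. It should be corrected before the data are analysed.

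**What to change.** In section 8.2:

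1. Analyse TICS-M, verbal fluency, WHODAS and GDS15 by ANCOVA, with the follow-up value as outcome and arm and baseline as terms. Use a bootstrap confidence interval if the residuals are skewed. This also settles the question of change versus final score.
2. Treat baseline adjustment as optional for DRS-R-98 and 3D-CAM-S, and state in advance whether it will be used.
3. Report all between-arm results, including incidence, EEG and biomarkers, as estimates with 95% confidence intervals, labelled exploratory.
4. Replace the sentence that declares P below 0.05 significant for all analyses with wording that matches item 3.

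The cost is a change of analysis wording and a little programming. No new data, visits or patients are needed.

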9. DATA COLLECTION

9.1. PARTICIPANT REGISTRATION

Participants will be registered/enrolled for the trial at the time of consent and will be provided with a study ID. The participant will be randomised to interventional group or placebo.

